The main objective of the study is to test the efficacy of a mental health intervention delivered via smartphone application in addition to brief CBT to reduce depressive symptoms and to promote maternal and child health and well-being in pregnant women with depression. Our primary outcome is the change in maternal prenatal depression from baseline to posttreatment (8 weeks). We will also test the efficacy of the intervention on secondary outcomes assessed during gestation: change in maternal mental health (prenatal anxiety, psychological well-being, perceived stress, depression, depression severity, and sleep quality) from baseline to posttreatment, change in maternal prenatal quality of life from baseline to posttreatment, and change in maternal physical activity levels from baseline to posttreatment. Additionally, we will conduct a postnatal follow-up when the child is 2 months of age to test the impact of the intervention on the following secondary outcomes: change in maternal mental health (postnatal depression symptoms, depression severity, anxiety, psychological well-being, perceived stress, and sleep quality) from baseline to follow-up, change in maternal postnatal quality of life from baseline to follow-up, infant developmental milestones, and social/emotional problems at 2 months of age.

Hypotheses

Participants receiving the Motherly app in addition to brief CBT will show significantly greater reduction in symptoms of depression, as well as greater well-being, better overall mental health, and levels of physical activity compared with participants who receive only educational content in addition to brief CBT. We also predict that children of mothers from the intervention group will show better development in the first two months of age in comparison with children from participants in the active control group.

Methods

Setting and design

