be required to respond to an online survey containing questions related to eligibility criteria of the study. Eligible participants will be invited to a baseline assessment which will be conducted via internet or telephone. In the baseline assessment, after obtaining informed consent, the participant will be instructed to download the Motherly and register a profile with basic information. Randomization will occur automatically in real time using PHP 7 rand function at the end of registration process [38]. After the first login the participant will already be using one of the two versions of the Motherly app (intervention or active control).

Participants cannot be blinded due to the nature of the intervention. Likewise, blinding of psychologists delivering brief CBT will not be possible. However, all assessments will be conducted by assessors blind to randomization and allocation status.

Assessments and instruments

All assessments will be conducted via the internet (videotelephony) or telephone. Assessment instruments as well as time points at which they will be used are shown in Figure 1. At baseline (T0), we will collect socio demographic information (socioeconomic status, educational level, occupation, income, etc) as well as frequency of use of smartphones, media, and apps. We will also conduct a comprehensive clinical assessment of maternal physical and mental health, perceived stress, personality traits, sleep quality, quality of life, physical activity frequency, and psychological well-being using the following instruments. We describe each instrument that will be used in the assessments below.

The Edinburgh Postnatal Depression Scale (EPDS), a 10-item scale developed to assess pre and post natal depression. It is the most used scale in studies about depression during pregnancy and the postnatal period, largely used in observational studies and clinical trials aiming to measure presence and severity of depressive symptoms. It has been validated for use in Brazil and used in multiple studies throughout the years [12, 39–41].

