Single-item sleep quality scale (SSQS), a 1-item scale (how would you assess the quality of your sleep) demonstrating high correlation with classical scales for assessing sleep problems in the literature, such as the *Pittsburgh Sleep Quality Index* (PSQI) and the *Morning questionnaire-insomnia* (MQI). Examinees can choose from 0 to 10, indicating his/her perception of the quality of sleep (from bad to excellent) [47]. Since the SSQS was not available in Brazilian Portuguese, we translated the scale to use in the present study.

The short version of the International Physical Activity Questionnaire (IPAQ) assesses daily physical activity. Twelve countries, including Brazil, participated in the validation of this scale. The IPAQ has been shown to be equivalent to other physical activity instruments and its data has been corroborated by objective measures via accelerometer, considered the gold-standard in the literature [48]. Its robustness allowed for the assessment of physical inactivity in a study conducted in 17 countries with a sample of 130,000 participants [49].

The Ryff's Psychological Well-Being Scale, an instrument developed by Carol Ryff based on the Aristotelian construct of eudaimonia and state of the art psychological theories of happiness and well-being [50–52]. This scale assesses six dimensions that compose the state of well-being with 36 items: Positive Relations With Others, Autonomy, Environmental Mastery, Personal Growth, Purpose in Life, and Self-Acceptance. The Ryff's Psychological Well-Being Scale was validated in Brazil [53].

The *12-item health survey* (SF-12) is a short version of the SF-36, a largely utilized scale to assess quality of life associated with health outcomes. It has a Likert scale format and assesses quality of life in two-domains: physical and mental health. We used the second version of the SF-12, previously validated to the context of the Brazilian population [54].

At mid-point (T1), we will conduct a comprehensive clinical assessment of maternal physical health, and assess depression (EPDS), anxiety (GAD-7), perceived stress (PSS), and quality of sleep (SSQS), as well as prenatal and health services use.

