Participants allocated to the active control group will have access to a simplified version of the app consisting of educational content about various aspects of pregnancy, maternal physical and mental health, and child development. Active intervention functionalities, such as behavioral activation, activity scheduling, sleep hygiene, among others, will not be present in this simplified version. As with the intervention group, participants from the active control group will receive app notifications to answer questions related to the outcomes of this study. The active control group will also receive four sessions of brief CBT throughout the 8 weeks, with a focus on BA. They will be guided by psychotherapists to plan, schedule, and engage in positively reinforcing activities, and will be aided to develop problem-solving strategies for circumventing barriers to completing scheduled activities. However, implementation of these techniques will be conducted without the aid of the Motherly app (as these functionalities are not present in the active control app). Throughout the four sessions, psychotherapists will monitor participants' adherence, answering questions about the strategies and providing support for solving problems or CBT techniques, such as cognitive restructuring, relaxation techniques, sleep hygiene, stress and anxiety management, among other evidence-based techniques might be used if appropriate to the case. The structure of the sessions will also follow the guide mentioned previously.

Sample Size

We calculated the sample size based on an expected effect size of 0.65 on depressive symptoms, which is based on a previous meta-analysis [115] (difference in means between two independent groups) considering a probability of type I error of 5%, statistical power of 80%, a two-tailed test, and a dropout rate of 15%.

Statistical analyses

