First, continuous variables will be described using central tendency measures and categorical variables will be described using frequencies and cross tabulations. To analyze the potential impact of the intervention on depression symptoms we will use an intention-to-treat (ITT) approach. To perform ITT analyses, we will use multiple imputation by chained equations to include every participant randomized. The effects of intervention on maternal depression (primary outcome) and secondary outcomes will be tested using a generalized linear mixed model for longitudinal data. Estimated marginal means will be extracted from these models to describe primary and secondary outcomes of the study for both groups. Marginal means will be used to plot data. Additionally, we will investigate the potential role of moderators (baseline characteristics, such as socioeconomic aspects and personality traits) of the treatment effect on outcomes using a regression-based approach [116]. Standardized effect sizes will be calculated from the difference between group means using criteria described by Cohen [117]. Tests will be considered significant at $p < 0.05$ and

Study protocol and statistical analysis plan

95% confidence intervals will be reported for all parameters. All analyses will be conducted using STATA 16 and R.

Data safety

All data from the assessments as well as clinical records from CBT sessions will be entered electronically via Research Electronic Data Capture (REDCap) [118], thereby ensuring safety of the data and protections of participants' information.

Staff

All assessments will be conducted by a team of psychologists with expertise in mental health and early childhood development with experience in clinical trials. Assessors will receive training sessions with a focus on presenting study details, as well as in-depth explanations of all instruments used. Brief CBT will be delivered by female psychologists with a certified specialization in CBT and previous experience in treating depression. In order to ensure fidelity and quality of treatment, psychotherapists will receive weekly supervision by a senior doctorate level clinical psychologist ([name]) with clinical background in CBT and BA.

Ethical issues and dissemination

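### The primary mixed model leaves the week-8 contrast, baseline EPDS adjustment and covariance unstated; pre-specifying an adjusted contrast costs about 2% of variance at worst (about 60 completers) and can gain much more

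*Combined protocol and SAP*

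**What the plan says.** Objectives and outcomes defines the endpoint: "Our primary outcome is the change in maternal prenatal depression from baseline to posttreatment (8 weeks"). It names no instrument. EPDS is the likely one, because it is the entry criterion, it heads the list of instruments as the perinatal depression scale, and it is collected at T0, T1 (midpoint) and T2 (week 8).

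Statistical analyses says that primary and secondary outcomes "will be tested using a generalized linear mixed model for longitudinal data", after multiple imputation by chained equations for everyone randomized. Marginal means are for description and plots. On effect size it says: "Standardized effect sizes will be calculated from the difference between group means". It does not say whether these are means of change or of level. Apart from description, its only stated use of baseline variables is as "moderators (baseline characteristics, such as socioeconomic aspects and personality traits) of the treatment effect on outcomes".

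Sample Size rests on a "difference in means between two independent groups", with an effect of 0.65 and no baseline correlation.

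On timing, Recruitment and randomization says: "In the baseline assessment, after obtaining informed consent, the participant will be instructed to download the Motherly and register a profile with basic information". It continues: "Randomization will occur automatically in real time using PHP 7 rand function at the end of registration process". No stratification is described. The order of the T0 EPDS and app registration is not given.

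**The concern.** A longitudinal mixed model is a family of analyses. At least three members fit the text:

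- **A.** Arm-by-visit with T0 as a free response. With complete data the week-8 contrast is essentially the difference in raw change. This is the most natural reading, given the outcome definition.
- **B.** A comparison of week-8 means. It is less natural, but it resembles the sample-size basis.
- **C.** A model that constrains the T0 mean to be equal across arms, which in effect adjusts for baseline.

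They have different standard errors. They also give different estimates whenever the arms differ at T0 by chance, and simple randomization does nothing to balance EPDS. If the contrast is not fixed in advance, it could be picked after the data are seen. The precision that T0 EPDS can offer, already planned for every woman, may also be lost.

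**Working it through.** **Inputs from the documents.** 70 women, 35 per arm; effect 0.65; two-sided 5%; 80% power; 15% dropout. Completers: 35 × 0.85 = 29.75, about 30 per arm.

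**Inputs assumed.** rho is the correlation of T0 with T2 EPDS, taken as 0.3, 0.5 and 0.7. k is T0 SD / T2 SD, taken as 1, 0.85 and 0.7. A k below 1 is possible because the EPDS entry threshold of 7 may narrow the T0 spread. T2 SD is set to 1, and 0.65 is read in T2 SDs.

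**The plan's own figure.** Per arm, n = 2(1.96 + 0.8416)² / 0.65² = 37.15, so 38. After dropout, 38 / 0.85 = 44.7, so 45 per arm or 90 in total. The stated 70 is not reproduced. That is a separate matter, and this point does not depend on it.

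**Large-sample variances** (common multiplier dropped):

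- raw change (A): 1 + k² − 2·rho·k
- week-8 means (B): 1
- adjusted for T0: 1 − rho²

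A minus adjusted is (k − rho)², which is never negative. Share of the raw-change variance removed, (k − rho)² / (1 + k² − 2·rho·k):

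| k | rho 0.3 | rho 0.5 | rho 0.7 |
|---|---|---|---|
| 1 | 0.49/1.40 = 35% | 0.25/1.00 = 25% | 0.09/0.60 = 15% |
| 0.85 | 25% | 14% | 4% |
| 0.7 | 0.16/1.07 = 15% | 0.04/0.79 = 5% | 0% |

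Against B the share removed is rho²: 9%, 25% and 49%, at any k. Against C with an adequate covariance it is 0%.

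**Small-sample cost.** Estimating one slope inflates the adjusted variance by (N − 3)/(N − 4). At N = 60 this is 57/56 = 1.018. It is 47/46 = 1.022 at N = 50 and 37/36 = 1.028 at N = 40. Adjustment therefore beats B only when rho² > 1/57, that is, rho above about 0.13. With equal SDs it beats A while 1 + rho < 2 × 56/57, that is, rho below about 0.96. Simulated ANCOVA at 30 per arm removes 34.5%, 23.5% and 12.7% of the raw-change variance at k = 1, and 13.7%, 3.5% and −1.7% at k = 0.7. A simulation of 70 women with T1 and T2 outcomes and about 15% missing at week 8 put the cost, when T0 carries no information, at 1.9% to 2.1%.

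**Power at 30 per arm** (noncentral t). Example at rho 0.5: the noncentrality for week-8 means is 0.65/√(2/30) = 2.517. Adjusted, it is 2.517/√(0.75 × 57/56) = 2.88.

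| Analysis | rho 0.3 | rho 0.5 | rho 0.7 |
|---|---|---|---|
| Raw change, k = 1 | 55% | 70% | 89% |
| Raw change, k = 0.7 | 67% | 80% | 93% |
| Week-8 means | 70% | 70% | 70% |
| Adjusted | 73% | 81% | 93% |

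**Room for choice.** With complete data, A and B differ by exactly the chance T0 imbalance. Its SD is √(2/30) = 0.26 T0 SDs. That is 0.258/0.65 = 40% of the planned effect with equal SDs, and 0.7 × 0.258/0.65 = 28% at k = 0.7.

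**Covariance** (simulated: T0/T1/T2, 30 per arm, complete data, exchangeable correlation, T1 SD midway). At k = 0.7, a common-T0-mean model with a plain random intercept has a model SE of 0.83 to 0.87 of the true SE and a type I error of about 9% to 11%. With equal SDs it is nominal. The free-T0 model with the same random intercept stays at 4.9% to 5.9% at k = 0.7. The unstructured common-T0-mean model gives 4.9% to 5.9% across all k and rho.

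**The case against.** The strongest reply is that an arm-by-visit contrast of change is valid under randomization, so adjustment is a choice about efficiency. That stands. A reader might infer that the planned test is biased or inflates type I error; the documents do not support this. The inflation found above belongs to a common-T0-mean model with a plain random intercept, which the wording permits but never mentions.

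Second, the gain over A rests on rho and k, which no document supplies, and it can vanish. This also stands. Nor should the larger gains against B carry the case: a week-8-only comparison sits badly with an outcome defined as change. It would also be wrong to say that adjustment beats B for any non-zero correlation; at this size it does so only above about 0.13.

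Third, the power figures use 30 completers per arm, whereas the plan imputes for all randomized. They are approximations to that analysis, and any fix has to cover the imputation model too.

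Fourth, EPDS as the primary instrument is an inference, and depression is also measured through the app.

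Fifth, a reader might infer from the midpoint list ("assess depression (EPDS), anxiety (GAD-7), perceived stress (PSS), and quality of sleep (SSQS), as well as prenatal and health services use") that other scales, such as physical activity, have only one post-baseline visit. The schedule is in Figure 1, which is not shown in the text available, so that cannot be settled here.

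What survives all five is the omission: no section supplies the contrast, the baseline term or the covariance.

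**Conclusion.** The point holds as a gap in pre-specification with a cheap improvement attached. It is not a flaw that invalidates the trial, but the plan should be changed. Against the most natural reading, adjusting for T0 EPDS removes about 35% to 15% of the variance with equal SDs and 15% to 0% at k = 0.7, for rho of 0.3 to 0.7. The worst loss is about 2% at about 60 completers, and slightly more with fewer completers or with missing week-8 data. Against a well-specified common-T0-mean model the benefit is pre-specification alone. These sizes assume EPDS as the primary instrument, one baseline covariate, a T0 value taken before randomization, and the ranges of rho and k shown. Confidence in the omission is high; confidence in the size of the gain is moderate.

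**What to change.** In Statistical analyses, state that:

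- the primary test is the arm difference in mean EPDS at T2, adjusted for baseline EPDS, from a model with categorical visit, arm-by-visit and baseline-by-visit terms, an unstructured covariance and small-sample degrees of freedom;
- T3 is, or is not, in this model;
- the standardized effect size comes from the same contrast;
- the chained-equations imputation model includes arm, baseline EPDS and all EPDS visits, and this contrast is pooled over imputations with small-sample degrees of freedom;
- if a common-T0-mean model is used instead, its covariance is unstructured and not a plain random intercept;
- secondary outcomes with a T0 value are adjusted for that value, with ANCOVA where Figure 1 shows a single post-baseline visit.

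Also name EPDS as the primary instrument, if that is intended. Confirm that the T0 EPDS is completed before the automatic randomization. If it is not, use the eligibility EPDS as the covariate, provided the screening survey records it.

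The cost is SAP wording and about one degree of freedom, or about 2% of variance at about 60 completers. No new data or visits are needed.
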